8. SAFETY ANALYSES

The safety analyses will be based on the “Safety” Population.

8.1. Adverse Events Analyses

The severity of AEs and SAEs will be determined by the investigator according to the US National Institute of Allergy and Infectious Diseases Division of Microbiology and Infectious Diseases (DMID, 2007a) criteria for adult toxicity assessment, except for serum creatinine adolescent (adolescent participants over 12 years of age and less than 18 years of age) laboratory data, which will be assessed using DMID pediatric toxicity criteria (DMID, 2007b). All reported AEs will be coded using MedDRA and summarized by system organ class (SOC) and preferred term (PT).

A treatment emergent AE (TEAE) is defined as an AE with start date/time after the first dose date/time of the study treatment. If the time part is missing, only dates will be considered. The number and percentage of TEAEs, study treatment-related AEs, SAEs, and AEs leading to study treatment or study withdrawal will be collected. Only TEAEs

will be included in summary Tables, but all AEs will be displayed in detailed subject Listings.

Adverse event severity is classified as mild (grade = 1), moderate (grade = 2), severe (grade = 3), potentially life threatening (grade = 4) or resulting in death (grade = 5). Adverse events starting after the first dose of study treatment with a missing severity will be classified as severe. If a participant reports an AE more than once within an SOC/PT, the AE with the worst-case severity will be used in the corresponding severity summaries.

Relationship to study treatment, as indicated by the investigator, is classified as “not related” or “related”. Adverse events with a missing relationship to study treatment will be regarded as “related” to study treatment. If a participant reports the same AE more than once within an SOC/PT, the AE with the worst-case relationship to study treatment will be used in the corresponding relationship summaries.

An overall summary of AEs will present the total number of adverse events reported and the number of participants in each treatment group who experienced at least one AE, AE by maximum severity grade, drug-related AE, non-serious AE, SAE, AE leading to discontinuation of study treatment, AE leading to withdrawal from study, and AEs of special interest (AESI).

Adverse events analyses including the analysis of AEs, SAEs and other significant AEs will be based on GSK Core Data Standards. All AEs, study drug related AEs, SAEs, and AEs leading to discontinuation of study treatment or withdrawal from study will be provided in separate Listings. The relationship between SOC and PT will be listed. Summary Tables will be provided by SOC, PT, and maximum severity grade.

In summary Tables where AEs are presented by SOC, PT, and maximum severity grade, SOC's will be sorted in descending order of the total incidence then alphabetically, PTs will be sorted in descending order of the total incidence then alphabetically within the SOC.

For completely missing or partial missing AE start date or end date, imputation rules will be applied following [Appendix 5](#).

In addition, a summary of the number and percentage of participants with common AEs, defined as AEs with $\geq 1\%$ incidence (before rounding) in any treatment group, will be presented in descending order of total incidence by PT. The incidence of common AEs with relative risk and associated 95% CIs will also be presented graphically for each treatment group.

AE summaries will also be presented for age subgroups (as recorded in the eCRF):

- Age: <18, 18-64, 65-74, ≥ 75

8.2. Adverse Events of Special Interest Analyses (AESI)

Cardiovascular (CV) AEs, gastrointestinal (GI) AEs, *C. difficile* AEs, and AEs related to Acetylcholinesterase Inhibition (AChE-I) as determined by algorithm will be considered AESIs.

8.2.1. *Clostridium difficile* AESIs

C. difficile AESIs (PTs *Clostridium difficile* infection and *Clostridium difficile* colitis) will be included in the overall summary of AEs. *C. difficile* laboratory testing results are collected and recorded on distinct eCRF pages, which will be presented in a separate subject Listing.

8.2.2. Cardiovascular and Gastrointestinal AESIs

GI AESIs are defined as AEs with a gastrointestinal SOC. Cardiovascular AESIs are defined as AEs with PTs that match the terms listed in Section 11.4.2.

For CV and GI AESIs, the number and percentage of participants with an event will be summarized by PT and the maximum grade. In addition, the incidence of AEs of GI effects and time to the first occurrence will be summarized. Graphical presentation of the cumulative distribution of time to the first GI event occurrence will be provided (participants with no occurrence will be regarded as censored at the last day of their participation in the study). The details of data displays are presented in Appendix 9.

8.2.3. Potential Acetylcholinesterase-Inhibition AESIs

Any reported AE listed in the Table below with a start time no later than 12 hours after the latest dose administered, as evaluated by the investigator as per the DMID grading criteria provided in protocol Section 10.13 Appendix 13: Division of Microbiology and Infectious Disease Adult Toxicity Tables for Adverse Event Assessment, will be included in the programmatic identification of a potential Acetylcholinesterase Inhibition (AChE-I) AESI.

List of preferred terms for programming to be considered potentially due to AChE-I is provided in Section 11.4.2.

Cumulative grade score of potential AChE-I events will be calculated as the sum of the grade of each reported AE. This enables the number of AEs and the severity of each AE to be taken into account. The grading scale is defined in Table 21.

Table 21 AChE-I Cumulative Grade Score Scale

Cumulative Grade:	0	1	2	3	4
Cumulative Grade Score:	0	1 to 3	4 to 6	7 to 10	≥11

For instance, if a subject reports two AEs, one of Grade 1 and the other of Grade 3 their cumulative grade score of 4 would result in cumulative grade 2, if a subject reports no AEs their cumulative grade score of 0 would result in cumulative grade 0. This will be calculated for All AChE-I events, non-GI AChE-I events and GI AChE-I events but only All AChE-I events and non-GI AChE-I events will be summarized.

AChE-I AESIs will be listed and tabulated by SOC, PT, and maximum severity grade. Non-GI AChE-I events will also be summarized. Separate Tables will summarize AChE-I AESI by number of events and unique PT. In addition, time of onset (time from first dose to the onset of first event in hours), duration, and lag time (the time from last dose to the end date/time of the last event for subjects whose end date/time of the last event is after treatment end date/time) of AChE-I events will also be summarized and repeated for non-GI AChE-I and GI AChE-I events. AChE-I events with a start time less than 6 hours after the latest dose administered will also be flagged in subject Listings.

Graphical presentation via a stacked bar charts of percentage of subjects in each AChE-I cumulative grade will be produced for All AChE-I events and non-GI AChE-I events separately. In addition, forest plots of the relative risk of AChE-I events between two treatment groups and the associated 95% CI for each event will also be constructed and displayed.

The details of the planned displays are provided in [Appendix 9](#).

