- j. Take measurement of temperature, blood pressure, and pulse rate.
- k. If serology testing was performed within 3 months prior to the first dose of study treatment and the results were **positive**, testing at Baseline is **not required**. If testing was performed within 3 months and any result was **negative**, testing at Baseline is **required**.
- l. For women of childbearing potential, a negative high sensitivity urine pregnancy test is sufficient for eligibility. See Appendix 8 for Baseline urine test sensitivity requirements and Appendix 2 for associated contraception requirements. Pregnancy testing should be performed after Dose 4 and before Dose 8, as specified in Appendix 8.

CCI

- n. Participants will receive oral study treatment twice daily for 5 days under double-blind, double-dummy conditions. The first oral dose will be administered at the study site during the Baseline Visit; participants will self-administer as outpatients thereafter, beginning with the second dose. Each dose should be taken after food consumption and with water. The date and time of each dose administered at the study site will be recorded in the source documents.

- o. At the On-therapy Visit, whenever it is possible, the participant will have the pregnancy test performed at the study site. If the visit coincides with the 8th dose, the participant will take their next dose of study treatment at the study site after negative pregnancy test results are confirmed. Note: The On-therapy Visit should be scheduled to support completion of the postdose ECG within the protocol-defined window. Also, in a woman of childbearing potential, the high sensitivity pregnancy test must be performed and show negative results at the latest before Dose 8 of study treatment is taken.
- p. Record serious adverse events from the time of consent/assent in order to fulfill international regulatory requirements.
- q. Record adverse events from the time of the first dose of study treatment.
- r. Determine study treatment compliance by performing pill count.
- s. Confirm return day/time for the On-therapy, TOC, and Follow-up Visits.
- t. Previsit reminder: Study site staff will contact the participant 24±4 hours before the scheduled On-therapy, TOC, and Follow-up Visits.
- u. Collect sample only if the participant has a signed consent/assent specific for this purpose. The Baseline Visit is the recommended time to collect the sample, but it can be collected at any time during the study.

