
Acetylcholinesterase Inhibition
 
In vitro testing showed gepotidacin to be a rapidly reversible inhibitor of acetylcholinesterase in the clinical plasma concentration range.
 
Based on clinical data, caution should be used in participants who have a condition requiring treatment with anticholinergic medications or who have certain medical conditions that may be exacerbated by the acetylcholinesterase inhibition activity of gepotidacin.
	
Increased cholinergic effects can potentially be associated with more severe symptoms including atrioventricular block, seizure/convulsions, bronchospasm, and vasovagal syncope. No causal relationship between these events and the use of gepotidacin has been established during clinical trials to date.
 
Adverse events consistent with acetylcholinesterase inhibition, including diarrhea, nausea, vomiting, gastrointestinal cramping and pain, dyspnea, bradycardia, lacrimation, salivation, and diaphoresis/sweating have been reported during clinical trials with gepotidacin.
 
Mild and transient non-gastrointestinal AEs have been associated with C_{max} levels higher than this dosing regimen.
	
Participants who have medical conditions or require medications that may be impacted by inhibition of acetylcholinesterase will be excluded from participation in this study. See Section 5.2 for excluded medical conditions and Section 6.5.2, Prohibited Medications and Nondrug Therapies, for prohibited medications.
 
Close monitoring of clinical parameters and AEs will be conducted to assess effects potentially related to acetylcholinesterase inhibition (Section 1.3).

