6.4. Study Treatment Compliance

- When participants are dosed at the study site during the Baseline and On-therapy Visits, they will take their study treatment when directed by the investigator or designee, under medical supervision. The date and time of each dose administered at the study site will be recorded in the source documents. The dose of study treatment and study participant identification will be confirmed at the time of dosing by a member of the study site staff other than the person administering the study treatment.
- When participants self-administer study treatment as outpatients, compliance with gepotidacin, nitrofurantoin placebo, nitrofurantoin, and gepotidacin placebo will be assessed through querying the participant during the study site visits and documented in the source documents and eCRF. A record of the number of gepotidacin and

gepotidacin placebo tablets and nitrofurantoin and nitrofurantoin placebo capsules dispensed to and returned by each participant must be maintained and reconciled with study treatment and compliance records. Study treatment start and stop dates, including dates for study treatment delays, will also be recorded in the eCRF.

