Periprocedural myocardial infarction	Wolff-Parkinson-White syndrome
Congenital pulmonary hypertension	Long QT syndrome
Portopulmonary hypertension	Parasystole
Deep vein thrombosis	Cardiac arrest neonatal
Revascularisation procedure	Neonatal sinus tachycardia
Cardiac failure congestive	Foetal tachyarrhythmia
Atrioventricular node dysfunction	Cerebrovascular disorder
Ventricular pre-excitation	Pulmonary arterial hypertension
Supraventricular tachyarrhythmia	Post procedural pulmonary embolism
Arrhythmia	Pulmonary microemboli

List of Cardiovascular AESIs Preferred Terms	
Cerebral revascularization	Supraventricular tachycardia
Timothy syndrome	Sinusoidal foetal heart rate pattern
Heart alternation	Bradycardia
Reperfusion arrhythmia	Tachycardia paroxysmal
Foetal heart rate disorder	Sinus tachycardia
Atrial parasystole	Wandering pacemaker
Atrial tachycardia	Withdrawal arrhythmia
Bifascicular block	Foetal heart rate acceleration abnormality
Atrioventricular block complete	Pacemaker syndrome
Sudden cardiac death	Structural valve deterioration
Sinus node dysfunction	Cardiac valve thickening
Sudden death	Post procedural myocardial infarction
Cardio-respiratory arrest	Pulmonary hypertension
Arrhythmia supraventricular	Obstetrical pulmonary embolism
Neonatal tachycardia	Heart block congenital
Bradycardia	Atrioventricular block second degree
Congenital heart valve incompetence	Extrasystoles
Cardiac valve rupture	Brugada syndrome
Heart valve calcification	Wolff-Parkinson-White syndrome congenital
Cardiac valve discolouration	BRASH syndrome
Cardiac valve vegetation	Ventricular arrhythmia
Congenital heart valve disorder	Foetal heart rate deceleration abnormality
Myocardial infarction	Long QT syndrome congenital
Silent myocardial infarction	Agonal rhythm
Septic pulmonary embolism	Frederick's syndrome
Coronary revascularization	Bradycardia neonatal
Atrioventricular conduction time shortened	Shone complex
Sinus arrhythmia	Transient ischaemic attack
Tachycardia	Cerebrovascular accident
Postural orthostatic tachycardia syndrome	

List of Acetylcholinesterase Inhibition AESIs Preferred Terms	
Abdominal discomfort	Generalised non-convulsive epilepsy
Abdominal pain	Generalised tonic-clonic seizure
Abdominal pain lower	Heart rate decreased
Abdominal pain upper	Hyperhidrosis
Abdominal symptom	Hyperkinesia
Abdominal tenderness	Hypocalcaemic seizure
Asthma	Hypoglycaemic seizure
Atonic seizures	Hyponatraemic seizure
Atypical benign partial epilepsy	Idiopathic generalised epilepsy

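### The SAP's acetylcholinesterase-inhibition (AChE-I) term list leaves out atrioventricular block and sinus bradycardia, so these events cannot enter the AChE-I displays; the dose-time rule also lacks a fallback

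*SAP*

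**What the plan says.** **Identification.** SAP 8.2 says AChE-I events are determined by algorithm. SAP 8.2.3 sets the rule for inclusion: "Any reported AE listed in the Table below with a start time no later than 12 hours after the latest dose administered". It sums the grades into a cumulative grade (Table 21) and tabulates all AChE-I and non-GI AChE-I events. It also summarises onset from the first dose, duration, and lag time from the last dose, and plots relative risks. A further rule reads: "AChE-I events with a start time less than 6 hours after the latest dose administered will also be flagged in subject Listings".

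**Term list.** The terms are in SAP 11.4.3 under "List of Acetylcholinesterase Inhibition AESIs Preferred Terms". SAP 8.2.3 points instead to a table below it and to Section 11.4.2, which is the Study Population section.

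**Cholinergic effects named in the protocol.** Protocol 2.3.1 states: "Increased cholinergic effects can potentially be associated with more severe symptoms including atrioventricular block, seizure/convulsions, bronchospasm, and vasovagal syncope". The same row lists bradycardia among events consistent with AChE inhibition that have been reported in gepotidacin trials.

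**Dose times.** For site doses, Protocol 1.3 (footnote n) and 6.4 say: "The date and time of each dose administered at the study site will be recorded in the source documents". For home doses, Protocol 6.4 describes participant query and counts of returned units, and adds: "Study treatment start and stop dates, including dates for study treatment delays, will also be recorded in the eCRF". SAP 11.5.2.1 sets a missing adverse event start time to midnight but has no rule for a missing dose time.

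**The concern.** The AChE-I displays are where a reader will look for the size and severity of the drug's cholinergic effect. If the list leaves out terms that the protocol itself ties to that effect, the displays understate it. The understatement concerns cardiac conduction and rate, the part a reviewer would most want to see counted. If the omitted events are drug effects, the shortfall would fall more on the gepotidacin arm.

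The timing rule raises a lesser question. A window in hours from a dose needs a clock time for that dose, and most doses are taken at home.

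**Working it through.** **1. Protocol effects against the SAP lists**

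| Effect in Protocol 2.3.1 | AChE-I list (SAP 11.4.3) | Cardiovascular list (SAP 11.4.3) |
|---|---|---|
| AV block | no term | Atrioventricular block; first degree; second degree; complete; Paroxysmal atrioventricular block |
| Seizure | many terms, including hypocalcaemic, hyponatraemic and hypoglycaemic seizure | not relevant |
| Bronchospasm | Bronchospasm; Unilateral bronchospasm | not relevant |
| Vasovagal syncope | Syncope | not relevant |
| Bradycardia | Bradycardia; Heart rate decreased | Bradycardia and, separately, Sinus bradycardia |

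Of the four severe effects, only AV block has no term. The cardiovascular list treats Sinus bradycardia as distinct from Bradycardia, so exact matching on the AChE-I list would miss it. That makes 5 + 1 = 6 missing terms.

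The terms do not look lost from the printed list. It is alphabetical and its neighbours are intact: Atonic seizures is followed by Atypical benign partial epilepsy, and Simple partial seizures by Status asthmaticus. One cell reads blank, but it lies between Syncope and Tonic clonic movements.

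**2. Effect on the cumulative grade**

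Table 21 maps scores 0, 1–3, 4–6, 7–10 and 11 or more to cumulative grades 0 to 4. The SAP's own example reproduces: 1 + 3 = 4, which is grade 2.

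- Grade 1 nausea plus Grade 3 AV block: score 1 (grade 1) with the present list; 1 + 3 = 4 (grade 2) with AV block added.
- The same participant in the non-GI display: score 0 (grade 0) now; score 3 (grade 1) with AV block added.

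**3. Doses with a described clock time**

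There are 10 doses (Protocol 6.5.2), about 12 hours apart (Protocol 6.1). Dose 1 is taken at the site. At most one more is, at the On-therapy Visit (SAP 2.3). That leaves 8 or 9 of 10 without a described clock time, normally including the last.

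**4. Where a missing dose time matters**

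On exact 12-hour dosing, dose 10 falls at 9 × 12 = 108 hours. The 12-hour window is then open without a break until 108 + 12 = 120 hours, so exact times change nothing before that point.

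Departures from schedule were simulated. Dose 1 was fixed, doses 2 to 10 had a normal error around nominal time, and event onset was uniform. The SDs and the onset distribution are assumptions. The entries are the share of events classified differently by true and by nominal 12-hourly times.

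| Dose-time SD | 12 h rule, 0–108 h | 12 h rule, 108–144 h | 6 h flag, 0–144 h |
|---|---|---|---|
| 0 h | 0% | 0% | 0% |
| 1 h | 4.3% | 2.9% | 9.8% |
| 2 h | 8.6% | 6.0% | 19.7% |
| 3 h | 12.8% | 9.1% | 28.0% |

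The errors before 108 hours are events in the gap before a late dose. The 6-hour flag is the more sensitive item.

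**5. The midnight rule**

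Suppose a listed event occurs on the day after an evening last dose at hour h, with no start time. The imputed gap is 24 − h hours. The share of that day truly within 12 hours of the dose is (h + 12 − 24)/24.

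- h = 18: gap 6 h, true share 25%.
- h = 20: gap 4 h, true share 33%.
- h = 22: gap 2 h, true share 42%.

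If only the stop date is known, the answer depends on a default that the SAP does not state. A dose set to 00:00 gives a 24-hour gap and exclusion; 23:59 gives one minute and inclusion.

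**The case against.** **No event is lost.** AV block and Sinus bradycardia are in the cardiovascular list, so they appear in Table 3.15 by term and maximum grade with no 12-hour condition, and in the overall Table 3.1. Protocol 2.3.1 says no causal relationship with AV block has been established. Placing a term in one list rather than both can be called a sponsor's choice. This stands as a limit on the harm. It does not remove the gap: SAP 8.2.2 gives cardiovascular events no cumulative grade or lag time, and the SAP states no reason for the omission.

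**Manual review.** Protocol 9.4.3 foresees manual as well as programmatic review of events of special interest. SAP 8.2 and 8.2.3 describe only the programmatic route, so the protocol's intention is not carried through.

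**Dose times.** A reader might infer that home-dose times are not recorded. The documents do not show that. The eCRF and the Study Reference Manual are not available here. SAP 11.2.1 refers to a treatment stop date and time, SAP 11.2.2 uses dosing time if collected, and SAP 11.3.2 plans listings of actual time relative to dosing. What stands is narrower: the documents describe clock times only for site doses and give no rule for a missing one.

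**Conclusion.** The term-list defect holds. Six terms that the SAP already uses elsewhere are missing, and one of the four severe effects named in Protocol 2.3.1 has no term. An affected participant's cumulative grade can be one level too low, as in the example. The documents give no incidence for these events, so the number of participants affected cannot be estimated.

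A reader might go further and call the AChE-I measure misclassified in general. The documents do not support that. With dosing about every 12 hours, the 12-hour window is nearly continuous from dose 1 to 12 hours after dose 10. A missing dose time matters after the last dose, around missed or late doses, and for the 6-hour flag and lag time. Time to onset is anchored on the site-given first dose, so missing home-dose times do not affect it.

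The displays are descriptive and the primary test is untouched. The double-dummy schedule is the same in both arms, so the design gives no reason for dose-time recording to differ between them.

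**What to change.** **Main change.** Before unblinding, add the five AV block terms and Sinus bradycardia to the AChE-I list in SAP 11.4.3. The cost is a list edit, a slightly broader definition, and some overlap with the cardiovascular table, which a footnote can explain.

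**Secondary change.** In SAP 8.2.3 and 11.5.2.1, name the source of home-dose times, or state a fallback for when they are missing. Two fallbacks are workable:

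- Nominal 12-hourly times from the recorded first dose. The simulated error is in the table above.
- Classification by date. Allowing events through the day after the last dose is simple but wider: a last dose at 22:00 gives 2 + 24 = 26 hours, and one at 08:00 gives 16 + 24 = 40 hours.

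Report the 6-hour flag and lag time only where times exist. This costs SAP wording and some loss of data on those two items. New eCRF fields are not clearly needed; added late, they would help only later participants or rest on long recall.

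**Tidying.** State whether the latest dose means the dose before the event or the final dose. Correct the references to the table below and to Section 11.4.2.
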